9.6.2 Clinical Data Management

All software applications used in the collection of data will be properly validated following standard computer system validation that is compliant with all regulatory requirements. All data, both CRF and external data (eg, laboratory data), will be entered into a clinical system.

9.7 Statistical Methods

All statistical analyses will be performed after the study is completed and the database is locked. Statistical analyses will be performed using SAS software or other validated statistical software as required.

9.7.1 Statistical and Analytical Plans

The statistical analyses of study data are described in this section. Further details of the analytical plan will be provided in the statistical analysis plan (SAP), which will be finalized before database lock.

9.7.1.1 Study Endpoints

The safety endpoints are AEs, clinical laboratory tests (biochemistry, hematology, and urinalysis), vital signs, weight, and 12-lead ECG.

The efficacy endpoint is the seizure frequency per day in each of the 3 phases (Pretreatment Phase, Treatment Phase, and Follow-up Phase). Seizure frequency per day will be derived from the information recorded in the subject diaries.

The pharmacokinetic endpoint is the plasma concentration of perampanel.

All observed data will be reported with no adjustments for missing data.

9.7.1.2 Definitions of Analysis Sets

The Safety Analysis Set is the group of subjects who received at least 1 intravenous infusion of perampanel.

The Efficacy Analysis Set is the group of subjects who received at least 1 intravenous

infusion of perampanel and had at least 1 postdose efficacy measurement.

The Pharmacokinetic Analysis Set is the group of subjects who received at least 1 intravenous infusion of perampanel and had at least 1 evaluable measurement of plasma perampanel concentration.

9.7.1.3 Subject Disposition

The number (percentage) of subjects who discontinued the Pretreatment Phase will be summarized for those who gave informed consent.

The number (percentage) of subjects who completed and discontinued the study will be summarized for those who received study drug.

In addition, the number of subjects who discontinued the study will be described according to the reason(s) for discontinuation.

9.7.1.4 Demographic and Other Baseline Characteristics

Demographic and other baseline characteristics for the Safety Analysis Set will be summarized using descriptive statistics. Continuous demographic and baseline variables include age, height, weight, and others (if necessary); categorical variables include sex, age group, and others (if necessary).

9.7.1.5 Prior and Concomitant Therapy

All investigator terms for medications recorded in the CRF will be coded to an 11-digit code using the World Health Organization Drug Dictionary (WHO DD). The number (percentage) of subjects who took prior and concomitant medications will be summarized in the Safety Analysis Set by Anatomical Therapeutic Chemical (ATC) class (ie, anatomical class, therapeutic class, pharmacologic class, and chemical class) and WHO DD preferred term.

Prior medications/non-pharmacological procedures will be defined as medications/non-pharmacological procedures that stopped before the start of doses of the study drug. Concomitant medications/non-pharmacological procedures will be defined as medications/non-pharmacological procedures that were used on or after the start of doses of the study drug. All medications/non-pharmacological procedures will be presented in subject data listings.

9.7.1.6 Efficacy Analyses

The efficacy analyses will be performed on the Efficacy Analysis Set.

The seizure frequency per day for each of the 3 phases (Pretreatment Phase, Treatment Phase, and Follow-up Phase) will be summarized using descriptive statistics (eg, mean, SD, median, minimum, and maximum). The seizure frequency per day from the Pretreatment Phase to the Follow-up Phase for each subject will be displayed using a

spaghetti-plot.

9.7.1.7 Pharmacokinetic, Pharmacodynamic, Pharmacogenomic, and Other Biomarker Analyses

9.7.1.7.1 PHARMACOKINETIC ANALYSES

The PK analyses will be performed on the Pharmacokinetic Analysis Set using the plasma concentrations of perampanel. Summary statistics for the plasma concentrations will be obtained by sampling time point and dose. The plasma concentrations of perampanel before and after switching from oral tablet to intravenous infusion will be plotted. A similar analysis may be conducted using dose-normalized plasma concentration data.

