8.2 Secondary Objectives

The secondary objectives of this study are:

- To evaluate the plasma concentration of perampanel before and after switching from oral perampanel to 30-minute intravenous infusions of perampanel
- To evaluate the seizure frequency before and after switching from oral perampanel to 30-minute intravenous infusions of perampanel

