9.1.2 Treatment Phase

The Treatment Phase is defined as the period beginning at the start of intravenous infusion of perampanel on Day 1 to immediately before the oral perampanel administration on Day 5.

Hospitalized subjects will be switched from oral perampanel on Day 1 to intravenous infusion of perampanel at a dose equivalent to the oral perampanel dose. Subjects will receive 30-minute intravenous infusions of perampanel once a day for 4 days under inpatient conditions (Days 1 through 4).

Subjects will be discharged from the hospital the day after the last intravenous infusion of perampanel (ie, Day 5), and treatment must be switched back to their original dose of oral perampanel.

If subjects cannot continue intravenous infusion of perampanel for any reason(s), they must discontinue the study.

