9.4 Treatment

9.4.1 Treatment Administered

The study drug, perampanel intravenous formulation, is a lyophilized powder for injection containing 8 mg of perampanel (anhydride) in a vial.

Subjects will be switched from oral perampanel (8 to 12 mg/day; stable-dosage treatment during the Pretreatment Phase) on Day 1 to intravenous infusion of perampanel at a dose equivalent to the oral perampanel dose. Subjects will receive 30-minute intravenous infusions of perampanel once a day in a supine position for 4 days under inpatient conditions (Days 1 through 4).

The start time of intravenous infusions of perampanel from Day 1 to Day 4 will be designated as the same time as the administration time of oral perampanel on Day –1 (allowance window: ± 1 hour).

As for the procedure for preparation of the intravenous infusion of perampanel, refer to the Instructions for Handling of Investigational Products provided by the sponsor.

Recording of Information Regarding the Study Treatment (Perampanel Intravenous Infusion)

The following information will be recorded in the CRF: Dose of perampanel; timing of dose (before/after a meal); planned intravenous-perampanel-infusion dose (mg); planned intravenous-perampanel-infusion volume (mL); actual intravenous-perampanel-infusion volume (mL); start date and time of infusion; end date and time of infusion; as well as date and time of both stopping infusion and resuming infusion, if applicable. In addition, if the intravenous-perampanel infusion is not performed as planned, the reason(s) will also be recorded on the CRF.

Recording of Information Regarding Oral Perampanel

Information regarding the oral perampanel will be obtained for the CRF. In addition, as for the administration time of the oral perampanel on Day –1, the day and time of the dose, as well as the timing of the dose (before/after a meal), will be recorded on the CRF.

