- g: During the period from Visit 3a to Visit 3d, if a subject experiences seizures or has safety issue, the investigator will make as judgment regarding study continuation/discontinuation based on the subject's tolerability and efficacy.
- h: Height is to be measured only at Visit 1.
- i: Blood samples for the plasma perampanel concentration will be collected at predose and at 0.5, 1, and 1.5 hours after the oral administration of perampanel on Visit 2 (Day -1), predose and at 0.5 hours after the start of intravenous infusions of perampanel on Visits 3a, 3b, 3c, and 3d (Days 1, 2, 3, and 4). In addition, for the blood samplings at 0.5 hours after the start of intravenous infusions of perampanel on Days 1 through 4, they should be performed immediately after completion of the intravenous perampanel infusions (ie, within 5 minutes after completion).
- j: All females of childbearing potential will undergo the serum β -hCG pregnancy test at Visit 1. At Visit 2 and thereafter, all females of childbearing potential will undergo the urine β -hCG pregnancy test.
- k: At an Unscheduled Visit, only the procedures/assessments that the investigator has judged as necessary according to the subject's condition will be performed.
- l: Subjects will be discharged from the hospital the next day following Day 4 (ie, on Day 5).
- m: The examinations will be conducted predose.
- n: The start time of intravenous infusions of perampanel from Day 1 to Day 4 will be designated as the same time as the administration time of oral perampanel on Day -1 (allowance window: ± 1 hour).
- o: As for subjects who have been withdrawn from the study, recording in the diary after discontinuation will continue as far as possible. Further, the investigator or the designated investigator's staff should record seizure counts and types on the CRF for up to 14 days after the subject's last intravenous infusion of perampanel.

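### Does the PK analysis miss its before/after objective by summarising concentrations by time point and dose, with no within-subject ratio?

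*Protocol*

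**What the plan says.** The secondary PK objective in protocol section 8.2 reads "To evaluate the plasma concentration of perampanel before and after switching from oral perampanel to 30-minute intravenous infusions of perampanel". Section 9.7.1.7.1 serves it with three items: "Summary statistics for the plasma concentrations will be obtained by sampling time point and dose"; a plot of concentrations before and after the switch; and an optional version of the same analysis on dose-normalised values. Section 9.7.1 defers further analytical detail to the SAP.

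The data come from Table 2, footnote i. On oral drug, samples are taken "predose and at 0.5, 1, and 1.5 hours after the oral administration of perampanel on Visit 2" (Day -1). On Days 1 to 4 they are taken before each infusion and at its end. Section 9.4.1 switches each subject "to intravenous infusion of perampanel at a dose equivalent to the oral perampanel dose", and for the Day -1 oral dose it has the CRF record "the day and time of the dose, as well as the timing of the dose".

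Section 9.7.1.2 defines the PK set by two conditions: at least one infusion received, and the subject "had at least 1 evaluable measurement of plasma perampanel concentration". Section 9.7.1.1 adds "All observed data will be reported with no adjustments for missing data". Under section 9.1.2, "If subjects cannot continue intravenous infusion of perampanel for any reason(s), they must discontinue the study". Section 9.7.2 sets the sample size of 20 by feasibility.

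**The concern.** The objective is a contrast between two routes, and each subject serves as his or her own control at an equivalent dose. Dose therefore cancels in a within-subject ratio, and all 20 subjects could be pooled. The stated summaries name no such ratio and divide 20 subjects among dose levels between 8 and 12 mg/day.

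The summaries could also rest on different people. One evaluable concentration on either side of the switch is enough for the PK set, subjects who cannot continue infusion leave, Table 2 marks no PK sample at the Early Discontinuation Visit, and missing values are not adjusted for. An apparent change after the switch could then partly be a change in who is being measured.

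Section 9.2 gives this some weight. Single-dose Cmax did not meet the bioequivalence criteria against the tablet, and the steady-state result that supports the 30-minute infusion is a simulation from a model fitted to healthy-subject data. Observed concentrations in patients on both routes are therefore of real interest.

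**Working it through.** The protocol gives no PK effect size, CV or precision target, so there is no figure to reproduce. The check has four parts. Every CV, cell size, loss count and half-life below is an assumption.

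**1. Do the planned summaries lose the paired estimate?** With the same n subjects at both time points,

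mean(log IV) − mean(log oral) = mean(log IV − log oral).

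The ratio of the two geometric means is therefore the paired geometric mean ratio. The same identity holds for differences of arithmetic means. It also holds within each dose level, because a subject keeps an equivalent dose across the switch. What the summaries alone do not give is an interval for the change and the individual changes.

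**2. What would pairing and pooling add in precision?** The log SD is √ln(1+CV²), and the half-width of a paired 90% interval is t(0.95, n−1) × SD × √(2/n). At a within-subject CV of 20% the SD is 0.198, and with a ratio of 1:

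| n | half-width | 90% limits |
|---|---|---|
| 20 | 0.108 | 0.90–1.11 |
| 10 | 0.162 | 0.85–1.18 |
| 7 | 0.206 | 0.81–1.23 |
| 4 | 0.330 | 0.72–1.39 |

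At n = 20 the limits are 0.92–1.08 for a CV of 15% and 0.85–1.17 for 30%. Pooling is tighter, as expected. But section 9.7.1.7.1 proposes no interval in any cell, so these figures describe a possible addition and not an error in what is planned.

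**3. Can the two sides hold different subjects?** The PK set requires an infusion as well as a concentration. Every member has crossed the switch, and is scheduled for all four Day -1 samples and for predose and end-of-infusion samples on Day 1. Apart from single missing or unevaluable samples, or a first infusion cut short, Day -1 against Day 1 end of infusion compares the same people. Dropout after Day 1 reaches only Days 2 to 4 of a four-day inpatient stay.

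Suppose 2 of 20 are lost at random, with no true change. The spurious log change has SD = SDb × √(1/18 − 1/20) = SDb × 0.0745.

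| Between-subject CV | SDb | SD of spurious change | 95% range, exp(±1.96 SD) | Both lost subjects one log SD high, exp(−SDb × 2/18) |
|---|---|---|---|---|
| 40% | 0.385 | 0.0287 | 0.95–1.06 | 0.96 |
| 60% | 0.555 | 0.0413 | 0.92–1.08 | 0.94 |
| 80% | 0.703 | 0.0524 | 0.90–1.11 | 0.92 |

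Nothing in the protocol supports a loss of two, or that those lost would have high concentrations. The calculation also pools all doses; within a small dose cell one lost subject would weigh more.

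**4. Would the added ratios settle the Cmax question of section 9.2?** Not directly. Oral sampling stops at 1.5 h, so the oral peak may not be observed, and a ratio to a fixed 0.5, 1 or 1.5 h value is not a Cmax ratio. Predose ratios are damped by oral carry-over. In a one-compartment model with a half-life from 100 h down to 24 h, the fraction of any eventual change seen is 1 − 0.5^(hours since switch / half-life): 15–50% at Day 2 predose (24 h), 28–75% at Day 3 and 39–88% at Day 4. A full set would be 4 days × 3 oral times = 12 end-of-infusion ratios plus 3 predose ratios, 15 in all. The choice of predose reference (Day -1 or Day 1) is itself open to argument.

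**The case for a change.** The strongest counter-argument is internal consistency. The protocol names change from baseline for laboratory values (9.7.1.8.3) and for vital signs and weight (9.7.1.8.4), and a per-subject plot for seizure frequency (9.7.1.6). The PK section has an explicit before/after objective, yet it names no change and does not say whether its plot shows individuals or means. A paired, pooled summary would need no new samples or visits, would be unaffected by who drops out among subjects with both values, and would put an observed figure beside the simulation in section 9.2.

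That stands as a case for a useful extra table. It does not show a fault. The plot in 9.7.1.7.1 may already be by subject, the optional dose-normalised analysis opens a way to combine doses, and nothing in the section rules out a paired summary. Which descriptive contrasts to tabulate, and which samples to match, is ordinary SAP content.

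**Conclusion.** The concern does not hold. In a study of 20 subjects sized by feasibility, with no inferential PK claim, summaries by time point and dose plus a before/after plot are a sound answer to a descriptive objective. With complete pairs the point estimate is the same either way.

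What remains is a preference for an interval and for individual changes. The possible distortion from dropout falls mainly on Days 2 to 4. Under the assumed random loss of 2 of 20 it stays within about 0.90 to 1.11, even at a between-subject CV of 80%.

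The conclusion rests on the PK set requiring at least one infusion, on Day -1 and Day 1 sampling being carried out as scheduled, and on the objective remaining descriptive. If the protocol claimed PK equivalence, or set a precision target, the lack of a stated paired estimate would need another look.

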9.7.1.7.2 PHARMACODYNAMIC, PHARMACOGENOMIC, AND OTHER BIOMARKER ANALYSES

Not applicable.

9.7.1.8 Safety Analyses

The safety analyses will be performed on the Safety Analysis Set.

Safety data will be summarized using descriptive statistics (eg, n, mean, SD, median, minimum, and maximum for continuous variables; n [%] for categorical variables). Safety variables include AEs, clinical laboratory parameters (biochemistry, hematology, and urinalysis), vital signs, weight, and 12-lead ECG results.

9.7.1.8.1 EXTENT OF EXPOSURE

The extent of exposure to the study drug will be summarized using descriptive statistics.

9.7.1.8.2 ADVERSE EVENTS

The AE verbatim descriptions (investigator terms from the CRF) will be classified into standardized medical terminology using the Medical Dictionary for Regulatory Activities (MedDRA). Adverse events will be coded to the MedDRA (Version 21.0 or higher) lowest level term (LLT) closest to the verbatim term. The linked MedDRA preferred term (PT) and primary system organ class (SOC) are also captured in the database.

A treatment-emergent adverse event (TEAE) is defined as an AE that emerges on or after the start of the study treatment, having been absent at pretreatment or

- Reemerges on or after the start of the study treatment, having been present at pretreatment but stopped before the start of the study treatment, or
- Worsens in severity on or after the start of the study treatment relative to the pretreatment state, when the AE is continuous.

All AEs, treatment-emergent or otherwise, will be presented in the subject data listings.

The incidences of TEAEs will be reported as the number (percentage) of subjects with TEAEs by SOC and PT. A subject will be counted only once within an SOC and PT,

even if the subject experienced more than 1 TEAE within a specific SOC and PT. The number (percentage) of subjects with TEAEs will also be summarized by maximum severity (mild, moderate, or severe).

The number (percentage) of subjects with treatment-related TEAEs will be summarized by SOC and PT. Treatment-related TEAEs include those events considered by the investigator to be related to the study treatment. The number (percentage) of subjects with treatment-related TEAEs will also be summarized by maximum severity (mild, moderate, or severe).

The number (percentage) of subjects with AEs by SOC and PT will be summarized by Phase (Pretreatment Phase, Treatment Phase, and Follow-up Phase) of onset.

Subject data listings of all AEs leading to death, all SAEs, and all AEs leading to discontinuation from the study will be provided.

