9.1.1 Pretreatment Phase

The Pretreatment Phase is defined as the period from Day -28 to immediately before intravenous infusion of perampanel on Day 1. On any day from Day -28 to Day -7, informed consent/assent will be obtained from the subjects, and the subjects will be screened.

Subject informed consent/assent will be obtained before the screening, and protocol eligibility will subsequently be established. Eligible subjects must be on a stable dosage (8 to 12 mg/day) of oral perampanel as an adjunctive therapy with 1 to a maximum of 3 marketed concomitant AEDs for at least 28 days before the first dose of the study drug (ie, intravenous infusion of perampanel).

Eligible subjects will return to and remain onsite (be “hospitalized”) 1 day before switching

from oral perampanel to intravenous infusion of perampanel (ie, on Day –1 [Visit 2]).

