9.1.3 Follow-up Phase

The Follow-up Phase is defined as the period after switching back to oral perampanel administration.

The assessments at the Follow-up Visit will be conducted 7 days (allowance window: +7 days) after the last intravenous infusion of perampanel.

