9.5.1.5.1 ADVERSE EVENTS

An AE is any untoward medical occurrence in a clinical investigation subject administered an investigational product. An AE does not necessarily have a causal relationship with the

medicinal product. For this study, the study drug is perampanel intravenous formulation.

The criteria for identifying AEs in this study are:

- Any unfavorable and unintended sign (including an abnormal laboratory finding), symptom, or disease temporally associated with use of an investigational product, whether or not considered related to the investigational product (Note: Every sign or symptom should not be listed as a separate AE if the applicable disease [diagnosis] is being reported as an AE)
- Any new disease or exacerbation of an existing disease
- Any deterioration in nonprotocol-required measurements of a laboratory value or other clinical test (eg, ECG or x-ray) that results in symptoms, a change in treatment, or discontinuation of the study drug
- Recurrence of an intermittent medical condition (eg, headache) not present pretreatment
- An abnormal laboratory test result should be considered an AE if the identified laboratory abnormality leads to any type of intervention, withdrawal of the study drug, or withholding of the study drug, whether prescribed in the protocol or not.

All AEs, regardless of relationship to the study drug or procedure, should be recorded in the CRF beginning from the time the subject signs the study ICF through the last visit and for 21 days after the subject's last dose of the study drug. Serious AEs will be collected for 28 days after the last dose of the study drug. In addition, the start date and time of an adverse event, and the end date and time of the adverse event will be recorded in the CRF.

Abnormal laboratory values should not be listed as separate AEs if they are considered to be part of the clinical syndrome that is being reported as an AE. It is the responsibility of the investigator to review all laboratory findings in all subjects and determine if they constitute an AE. Medical and scientific judgment should be exercised in deciding whether an isolated laboratory abnormality should be classified as an AE. Any laboratory abnormality considered to constitute an AE should be reported on the CRF.

All events associated with suicidal ideation/attempt, regardless of severity, must be recorded as an AE in the CRF.

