9.5.1.5.3 STUDY-SPECIFIC ADVERSE EVENTS

In a non-clinical toxicity study of sodium sulphobutylether-beta-cyclodextrin (hereinafter “SBECD”), which is one of the additives in this study drug, vacuolation was observed in tubular epithelial cells, suggesting that patients with impaired renal function have a risk of SBECD accumulation (Luke, et al., 2010). In addition, there have been reports of anaphylaxis, possibly due to SBECD, with other formulations containing SBECD.

In this study, based on the above findings, adverse events associated with renal dysfunction, and adverse events associated with anaphylaxis will be handled as “adverse events of special interest (AESIs)” and recorded in the CRF.

For the procedures for reporting adverse events of special interest, see Section 9.5.4.3.2

1. Adverse Events Associated With Renal Dysfunction

If an adverse event associated with renal dysfunction occurs, and does not resolve at the time point when the Follow-up Phase is completed, the investigator will monitor the subject for 14 days from the follow-up visit, regardless of severity, and will continue following up the subject as needed until resolution of the event or, if resolution is unlikely, until stabilization of the symptom or sign. During this period, the subject will be followed up continuously by renal function monitoring at unscheduled visits (eg, once weekly, or at a frequency deemed necessary by the investigator).

2. Adverse Events Associated With Anaphylaxis

In the event of an adverse event associated with anaphylaxis, the investigator will take the following responsive actions:

- Take the first response, for example, by immediately referring the subject to an appropriate clinical department;
- Make a decision regarding whether or not to continue administration of the study drug to the subject, based on advice from the physician in the above-mentioned department;
- In the event of an adverse event associated with anaphylaxis while continuing intravenous administration of the study drug, discontinue the administration. In the event of any symptom or sign that is suspected of anaphylaxis while continuing intravenous administration of the study drug, careful judgment will be exercised in determining whether or not to continue the administration.

The follow-up of anaphylaxis will be continued until resolution of the event or, if resolution is unlikely, until stabilization of the symptom or sign.

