9.5.2 Schedule of Procedures/Assessments

9.5.2.1 Schedule of Procedures/Assessments

Table 2 presents the schedule of procedures/assessments.

Table 2 Schedule of Procedures / Assessments in Study E2007-J081-240

Phase	Pretreatment Phase		Treatment Phase ^a				Follow-up Phase ^{b, c}	Unscheduled Visit ^k	Early Discontinuation Visit
	Day -28 to -7 (Screening)	Day -1	Day 1	Day 2	Day 3	Day 4			
Study Day(s) (from Day 1 of Treatment Phase)							7 days after the last intravenous infusion		
Visit	1	2	3a	3b	3c	3d		4	
Procedure/Assessment									
Informed consent/assent ^d	X								
Inclusion/exclusion criteria	X	X	X						
Physical examinations	X	X	X ^m	X ^m	X ^m	X ^m	X	X	X
Medical history	X								
Concomitant medications/therapies	X ^e	X ^e	X ^e	X	X	X	X	X	X
Hospitalization		X	X	X	X	X ^l			
Intravenous administration of the study drug (intravenous infusion of perampanel)			X	X ⁿ	X ⁿ	X ⁿ			
Oral perampanel administration at the hospital		X ⁿ							
Adverse events ^f	X	X	X	X	X	X	X	X	X
Oral perampanel/study drug compliance	X	X	X	X	X	X	X		X
Dispense subject diary	X		X			X			X
Return and review subject diary			X			X	X ^o		X
Discontinuation/continuation judgment ^g		X	X	X	X	X			
Vital signs and weight/height ^h	X	X	X ^m	X ^m	X ^m	X ^m	X	X	X
Clinical laboratory evaluations	X	X				X ^m	X	X	X
PK blood sampling for perampanel ⁱ		X	X	X	X	X			
Urine drug screen	X								
Urine pregnancy test ^j		X					X	X	X
Serum pregnancy test ^j	X							X	
12-lead ECG	X	X				X ^m	X	X	X

- a: The date of each visit to be specified based on the date of Visit 3a. The Treatment Phase is defined as the period beginning at the start of the study treatment (intravenous infusion of perampanel) on Day 1 to immediately before the oral perampanel administration on Day 5.
- b: Visit to be performed within +7 days of the schedule. The visit is to be specified based on the date of the last intravenous infusion of perampanel.
- c: To be completed by subjects who received at least 1 intravenous infusion of perampanel, in principle.
- d: Informed consent must be obtained before any study-related procedure.
- e: Prior and concomitant medication(s)/therapies(s).
- f: Adverse events will be collected from the time the subject signs the informed consent form through the 21 days after the subject's last intravenous infusion of perampanel. Serious adverse events will be collected for 28 days after the subject's last intravenous infusion of perampanel.

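### AEs by phase of onset are shown as crude subject percentages over unequal observation windows, so at equal daily risk and equal ascertainment the 4-day IV phase has the lowest expected figure

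*Protocol*

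**What the plan says.** Section 9.7.1.8.2 lists the AE summaries. TEAEs and treatment-related TEAEs are tabulated by SOC and PT and by maximum severity, pooling all onsets from the first infusion onward. One further table splits onsets by phase: "The number (percentage) of subjects with AEs by SOC and PT will be summarized by Phase" (Pretreatment, Treatment, Follow-up) of onset. No time denominator is given for it.

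The three windows are set elsewhere in the protocol:

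- **Pretreatment.** AE recording starts at consent (Section 9.5.1.5.1). Section 9.1.1 says "On any day from Day -28 to Day -7, informed consent/assent will be obtained from the subjects".
- **Treatment.** Section 9.1.2 defines it as "the period beginning at the start of intravenous infusion of perampanel on Day 1 to immediately before the oral perampanel administration on Day 5". The synopsis gives this as 4 days.
- **Follow-up.** Section 9.1.3 says "The Follow-up Phase is defined as the period after switching back to oral perampanel administration". It gives no end. It then times the visit: "The assessments at the Follow-up Visit will be conducted 7 days (allowance window: +7 days) after the last intravenous infusion of perampanel". Footnote f of Table 2 reads "Adverse events will be collected from the time the subject signs the informed consent form through the 21 days" after the last infusion; SAEs are collected for 28 days.

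For the same three phases, Section 9.7.1.1 defines the seizure endpoint as a frequency per day.

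**The concern.** The chance that a subject has at least one AE rises with the number of days observed. A percentage from 4 days and a percentage from two or three weeks are not on the same scale, even if daily risk is identical.

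The study has no control group, and its primary objective (Section 8.1) is the safety and tolerability of the infusions after switching from oral drug. The subjects' own oral periods are the only within-study context for AEs on IV drug. The pooled TEAE tables cannot supply it, because they mix the IV days with days back on tablets. A reader who turns to the by-phase table may take a lower IV percentage as a sign of good tolerability when it reflects a short window. A genuine rise in daily AE risk on IV drug could be hidden in the same way.

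**Working it through.** The protocol states no AE rate or expected percentage, so there is no figure of its own to reproduce.

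**1. Window lengths.** Section 9.1.1 places Day -1 one day before the Day 1 switch, so there is no Day 0.

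- Pretreatment: consent on Day -7 gives 7 days before Day 1; consent on Day -28 gives 28 days. The length varies by subject.
- Treatment: Day 1 infusion to the Day 5 oral dose, 4 days.
- Follow-up to the end of AE collection: last infusion on Day 4 plus 21 days is Day 25. From Day 5 that is 20 elapsed days, or 21 if both end days are counted. SAE collection runs to Day 32.
- The Follow-up Visit falls on Day 11 to Day 18 (4 + 7 to 4 + 14).

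**2. Expected percentage at equal risk.** With constant daily hazard h over t days, P(at least one AE) = 1 − exp(−h × t). The values of h are assumptions; the protocol gives none.

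| h per day | 4 d (IV) | 7 d | 14 d | 21 d | 28 d |
|---|---|---|---|---|---|
| 0.01 | 3.9% | 6.8% | 13.1% | 18.9% | 24.4% |
| 0.02 | 7.7% | 13.1% | 24.4% | 34.3% | 42.9% |
| 0.05 | 18.1% | 29.5% | 50.3% | 65.0% | 75.3% |

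The 4-day column is lowest in every row.

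**3. Daily rate ratio at which the percentages are equal.** Equality needs h(IV) × 4 = h(other) × t, so the ratio is t/4 whatever the hazard.

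- Against Pretreatment: 7/4 = 1.75 to 28/4 = 7.
- Against Follow-up run to the end of AE collection: 20/4 = 5.0 to 21/4 = 5.25.

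**4. Chance with 20 subjects.** Simulation: 200,000 trials, 20 subjects per phase, phases treated as independent, equal daily risk. It gives the probability that the observed IV percentage is strictly the lowest.

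| Windows (Pre/IV/Follow-up, days) | h = 0.02 | h = 0.05 |
|---|---|---|
| 7/4/7 | 0.45 | 0.61 |
| 18/4/20 | 0.94 | 0.995 |
| 28/4/21 | 0.97 | 0.999 |

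The first row uses the earliest permitted consent-to-Day-1 gap and a Follow-up cut at the earliest visit; there the order is far from certain. If IV daily risk is doubled with windows 18/4/20 and h = 0.02, the expected percentages are 30.2%, 14.8% and 33.0%. The IV phase still looks lowest.

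**5. What a rate can deliver.** IV time is 20 × 4 = 80 subject-days. Exact Poisson 95% limits: 2 AEs give 2/80 = 0.025 per day (0.003 to 0.090); 0 AEs give an upper limit of 0.046 per day.

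**The case against.** The strongest reply is that this is an ordinary descriptive table. Section 9.7.1 leaves further detail to an SAP that is not shown, and that SAP could add rates. Safety is not framed as a before-and-after comparison: Section 8.2 reserves that wording for plasma concentration and seizure frequency, so scaling seizures per day but not AEs fits the objectives. The 4-day length is stated openly, all AEs are listed by subject, and with 20 subjects a careful reader can see what is happening. Closer inpatient observation may also raise the IV figure and work against the window effect.

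Much of this stands. It limits the point to how one table reads and makes the result conditional on equal ascertainment. It does not change the fact that the protocol itself fixes the measure as a subject percentage by phase, and that this measure depends on window length.

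Two stronger readings are tempting and should not be drawn.

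- A reader might infer that the open Follow-up end could reverse the order of IV and Follow-up rates in the same data. That requires holding the Follow-up AE count fixed while lengthening the window. A longer window would also gather more AEs, and any table produced will apply one rule.
- A reader might infer that late AEs fall in no phase, because the renal-event text in Section 9.5.1.5.3 speaks of an event unresolved "at the time point when the Follow-up Phase is completed, the investigator will monitor the subject for 14 days from the follow-up visit", as if the phase closed at that visit. That is a monitoring instruction. The definition in Section 9.1.3 is open-ended and, taken as written, places every AE after the switch back to tablets in Follow-up.

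**Conclusion.** The point holds as a reporting weakness worth correcting. It does not threaten the study's validity. The by-phase percentages cover about 7 to 28 days, 4 days, and up to about 21 days (28 for SAEs). At equal constant daily risk and equal ascertainment, the IV phase has the lowest expected percentage. The IV daily rate would have to be about 1.75 to 7 times the Pretreatment rate, and about 5 times the Follow-up rate if that phase runs to the end of AE collection, before the percentages met.

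The ratios rest on the protocol's day counts and a constant hazard; the percentages and simulated probabilities also rest on assumed hazards of 0.01 to 0.05 per day. The statement is about expectation. It would be too strong to say the IV column will be lowest, because with the shortest windows chance often changes the order. Nor do the documents support saying that a phase comparison is planned or tested.

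**What to change.** Keep the n (%) table and the full-window TEAE tables. Then:

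1. State that, for AE attribution, the Follow-up Phase runs to the end of AE collection (21 days after the last infusion), with SAEs collected after that day identified separately.
2. For each phase, add the subject-days observed and the AEs per subject-day with exact Poisson 95% CIs. Subjects with a first AE per subject-day at risk is an alternative that avoids repeat events.
3. Add a note that monitoring intensity differs by phase (inpatient while on IV drug) and that daily risk may not be constant.

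The cost is one sentence, two rows and a note. No new assessment is needed: Section 9.5.1.5.1 already requires that "the start date and time of an adverse event, and the end date and time of the adverse event will be recorded in the CRF", and Section 9.4.1 records infusion start and end times. Section 9.4.1 asks for a clock time of the oral dose only on Day -1, so the Treatment/Follow-up boundary may have to be set by date.

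The downside is imprecision. At about 80 IV subject-days, no AEs at all is still compatible with 0.046 per day, and Poisson intervals are too narrow if AEs cluster within subjects. The rates put the columns on one scale; they will not establish or exclude a moderate increase on IV drug.
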